12.1 Adverse Events

12.1.1 General Methodology for Adverse Events

Unless otherwise specified, tables, and graphs will be based on the APTS. Listings will be based on the APES.

All the tables will be presented for the total group. Three tables will be split by previous treatment as well, see section [12.1.6](#) and [12.1.9](#).

Unless otherwise specified, the summaries of adverse events will include the number and percentage of patients with an adverse event.

Only stop-dates for ongoing events at the Primary Outcome/Withdrawal Visit, and new SAEs are collected in the Follow-up Period. Therefore, adverse events in the Follow-up Period will be included in the summaries for the Treatment Period (periods are defined in section [12.1.3](#)).

Listings of adverse events will be sorted by site, previous treatment group, patient screening number (from the extension study), and adverse event start date, and include preferred term, investigator term, adverse event start date, days since first dose of IMP, duration of the adverse event, date of death, action taken, causality, intensity, seriousness, and outcome. For adverse events that change in intensity/seriousness, each intensity/seriousness will be

included. Imputed adverse event start dates (see section 19.3.5) will be included in the listings, where information about the imputation will be included as a flag in the end of the date (M = month and day imputed or D = day imputed).

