- The Safety Follow-up Visit will be done 6 weeks (+3 days) after the last dose of IMP. This visit can be a telephone contact, unless an SAE has occurred since last visit or unless there was a clinically significant abnormal safety laboratory test value at the last visit. In such cases, safety follow-up(s) must be scheduled to allow for a medical examination and/or blood sampling. Further Safety Follow-up Visits beyond 6 weeks may be needed as judged by the

- investigator (if further Safety Follow-up Visits are performed, these must be recorded in the patient's medical record, and not in the CRF).
- e. If the date of a patient visit does not conform to the study plan, subsequent visits should be planned to maintain the visit schedule relative to the Baseline Visit. The number of days between 2 visits should not exceed the number of days for which the patient has been dispensed IMP.
  - f. For *16159A-patients* and *16323A-patients*, the data will be linked respectively from the Screening Visit in the study 16159A eCRF or from the Screening Visit in the study 16323A eCRF, when applicable.
  - g. For *16159A-patients* and *16323A-patients*, results from effectiveness/safety assessments and blood/urine samples performed respectively at the Primary Outcome Visit (Visit 12) in study 16159A or at the last day of the dosing period (Day 42) in study 16323A (when available) will be linked to the Baseline Visit (Visit 1) in study 16159B, when applicable.
  - h. For *16159A-patients*, HEA data will be linked from the Baseline A Visit in the study 16159A eCRF.
  - i. To be performed only for newly recruited patients not previously participating in a study investigating Lu F35700.
  - j. Exploratory gene expression profiling (RNA) and metabolomics/proteomics are covered by the main Patient Information Sheet.
  - k. Sampling for pharmacogenetics is optional and a separate Patient Information Sheet covers this analysis. This sampling should preferably be at the Baseline Visit, but may be collected at any visit that includes a clinical safety laboratory sample.
  - l. For *16159A-patients* and *16323A-patients*, ongoing adverse events from study 16159A and 16323A, respectively, are to be transferred by the investigator to the eCRF, when applicable.
  - m. Only for adverse events ongoing at the Primary Outcome/Withdrawal Visit and new SAEs.
  - n. Only to be taken if the laboratory test was clinically significantly abnormal at the Primary Outcome/Withdrawal Visit.

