#### **6.6 Post -study Access to IMP**

Post-study access to IMP will not be available. Patients in the study will have access to appropriate medical care after they complete or withdraw from the study.

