Recent and concomitant medication will be coded using the *WHO Drug Dictionary* (WHO-DDE).

Medications will be classified according to the start and stop time and summarized by anatomical therapeutic chemical (ATC) code levels 2 and 3, generic drug name, previous treatment group, and for each of the categories:

- Medication started before first dose of IMP (i.e. on-going concomitant medication from the lead-in study) and continued after first dose of IMP
- Concomitant medication started at or after first dose of IMP

The tables will be based on the APTS.

10 Exposure and Compliance

Exposure (days) to IMP in study 16159B will be calculated as:

$$\text{Last date of IMP} - \text{Start date of IMP} + 1$$

For details about handling of missing IMP start or stop date, see section 19.3.1 (IMP Start and Stop Dates).

The exposure for patients on the weekly dosing regimen will be summarized together with the exposure for patients on the daily dosing regimens.

Exposure to IMP will be summarized overall and by previous treatment group using descriptive statistics, and summaries will include the patient years of exposure (PYE). PYE will be calculated as the sum of the number of days of exposure to IMP for each patient, divided by 365.25 days.

In addition, exposure to IMP will be categorized in intervals 1 – 84 days [0 – 3 months], 85 – 168 days [3 – 6 months], 169 – 252 days [6 – 9 months], 253 – 336 days [9 – 12 months], > 336 days [>12 months], and summarized overall and by previous treatment group.

The final dose level for patients in APTS will be summarized overall and by previous treatment group.

The number of patients switching to the weekly dosing regimen will be summarized based on the APTS. The summary will include the number of patients going back to daily dosing after initiating weekly dosing.

Non-compliant days are days on which no IMP has been taken, less than the full dose of IMP has been taken, or more than the full dose of IMP has been taken.

Compliance (%) with IMP for the Treatment Period will be calculated as:

$$\frac{\text{Last date of IMP} - \text{Start date of IMP} + 1 - \text{Number of non-compliant days}}{\text{Last date of IMP} - \text{Start date of IMP} + 1} \times 100$$

where the number of non-compliant days is defined as the sum of all non-compliant days from the start of the interval to the end of the interval.

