12.1.4 Allocation of AEs to Treatment Periods

AEs will be allocated to treatment periods according to the time of onset of the adverse event (for handling of incomplete start dates, see section 19.3.5):

- *AE in Lead-in Study Period* – an AE that starts before first dose of IMP in study 16159B
- *AE in the Treatment Period* – an AE that starts at or after the date of first dose of IMP in study 16159B and at or before the date of the Primary Outcome/Withdrawal Visit
- *AE in the Safety Follow-up Period* – an AE that starts after the last visit in the Treatment Period

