12.1.5 Presentation of Adverse Events

All adverse events will be listed for the APES, including a flag for TEAEs. A listing of all AEs occurring while on weekly dosing will also be presented.

An overview of the PYE, number and percentages of patients with TEAEs, serious adverse events (SAEs), TEAEs leading to withdrawal, and of patients who died will be provided based on the APTS. For TEAEs, SAEs, and adverse events leading to withdrawal, the total number of events will be included.

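### SAE and death summaries labelled Treatment Period also count SAEs from up to 42 days of follow-up, beside a PYE that ends at the last dose, and no planned table separates the two

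*SAP*

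**What the plan says.** **Collection.** SAP 12.1.1: "Only stop-dates for ongoing events at the Primary Outcome/Withdrawal Visit, and new SAEs are collected in the Follow-up Period". Footnote m of Protocol Panel 2 has the same rule for the Safety Follow-up Visit: "Only for adverse events ongoing at the Primary Outcome/Withdrawal Visit and new SAEs".

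**Pooling.** SAP 12.1.1 gives this collection rule as its reason and concludes that "adverse events in the Follow-up Period will be included in the summaries for the Treatment Period". For the period definitions it points to 12.1.3, which is the section on MedDRA coding; the definitions are in 12.1.4.

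**Periods.** SAP 12.1.4 ends the Treatment Period at the Primary Outcome/Withdrawal Visit and defines an event in the Safety Follow-up Period as "an AE that starts after the last visit in the Treatment Period". None of the summaries in 12.1.5 to 12.1.10 uses that second category. The TEAE definition (SAP 12.1.2, Protocol 17.9.1) opens at the first dose and has no closing date.

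**Exposure.** In SAP section 10, exposure runs from the first to the last IMP date, and "PYE will be calculated as the sum of the number of days of exposure to IMP for each patient", divided by 365.25.

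**Display.** SAP 12.1.5 plans "An overview of the PYE, number and percentages of patients with TEAEs, serious adverse events (SAEs), TEAEs leading to withdrawal" and of patients who died, with total event counts added for TEAEs, SAEs and events leading to withdrawal.

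**The concern.** Adverse events are a primary endpoint of a study whose primary objective is long-term safety, so the window behind each count should be plain. Three windows meet in one overview:

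- SAEs and deaths: first dose to 42 days after the last dose.
- New non-serious events: first dose to the last treatment visit.
- PYE: first dose to last dose.

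The SAP's reason for pooling is that follow-up collection is limited to SAEs. That argues for showing those SAEs apart, because merging them gives one event class a longer observation time than the other. It also differs from SAP 12.2, which leaves the safety follow-up visit out of the last-assessment and PCS summaries.

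What happens in those weeks matters to the reader. Protocol 6.6 says "Post-study access to IMP will not be available", and patients return to usual practice. Hospitalisation is an SAE criterion (Protocol 10.1.1), so a relapse admission in follow-up, or a serious event on a later antipsychotic, would be tabulated as a treatment-emergent SAE. A reader of the tables could not tell how many SAEs began on treatment.

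**Working it through.** **Inputs from the documents**
- Treatment 52 weeks (364 days), follow-up 6 weeks (42 days): SAP 3.2.
- More than 500 patients included: SAP 16; 500 is used here.
- Planned completion 200 of 400, or 50%: Protocol 5.1.
- Half-lives 143 h (parent) and 250 h (metabolite): Protocol 1.1.5.2.

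**Assumptions.** The documents do not give the mean exposure E, the SAE hazard in follow-up relative to treatment (h), or the completeness of follow-up. Completion is varied from 50% to 100%, and mean exposure in withdrawn patients from 91 to 182 days. Every patient is taken to be followed for 42 days.

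**1. The plan's own figure.** 52 + 6 = 58 weeks, which matches SAP 3.2. This is the longest window for SAEs and deaths, against at most 52 weeks in PYE.

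**2. Time observed for SAEs but left out of PYE.** 500 × 42 / 365.25 = 57.5 patient-years.

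**3. A rate formed from the overview.** Pooled SAEs divided by PYE, relative to the on-treatment rate, is 1 + h × 42 / E. With h = 1:

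| Assumption | E (days) | PYE = 500 × E / 365.25 | Ratio |
|---|---|---|---|
| All complete | 364 | 498.3 | 1 + 42/364 = 1.115 |
| 50% complete, others average 182 days | 0.5 × 364 + 0.5 × 182 = 273 | 373.7 | 1 + 42/273 = 1.154 |
| 50% complete, others average 91 days | 0.5 × 364 + 0.5 × 91 = 227.5 | 311.4 | 1 + 42/227.5 = 1.185 |

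With E = 273, h = 0.5 gives 1.077, h = 2 gives 1.308 and h = 3 gives 1.462.

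**4. The planned scale, percentage of patients.** For a completer with constant hazard λ, incidence is 1 − exp(−λ × days / 365.25), over 364 versus 406 days:
- λ = 0.05 per year: 4.9% versus 5.4%
- λ = 0.10 per year: 9.5% versus 10.5%
- λ = 0.20 per year: 18.1% versus 19.9%

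**5. Residual drug after the last dose.** Remaining fraction = 0.5^(24 × days / half-life in hours):

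| Days after last dose | Parent | Metabolite |
|---|---|---|
| 7 | 44% | 63% |
| 14 | 20% | 39% |
| 42 | 0.8% | 6.1% |

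Five half-lives are 5 × 143 / 24 = 29.8 days (parent) and 5 × 250 / 24 = 52.1 days (metabolite). Early follow-up still carries exposure; by its end the drug has largely cleared.

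**6. Cut-offs.** The Treatment Period in 12.1.4 ends at the last visit, while PYE ends at the last dose. Splitting by the 12.1.4 periods alone would still leave events between last dose and last visit outside the PYE window.

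**The case against.** Much of the case on the other side stands.

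- **No planned rate is wrong.** A reader might infer that the study will report inflated SAE rates. The SAP specifies numbers and percentages of patients, with event counts, and nowhere a rate per PYE. The excess in step 3 arises only if someone divides the overview's counts by its PYE. The percentages are valid as incidences over up to 58 weeks.
- **Off-drug relapse is possible, not documented.** A reader might infer that the tables are filled with events unrelated to exposure. The half-lives do not support that. The metabolite also has a similar, though less potent, profile (Protocol 1.1.2), and CPK rises in the earlier multiple-dose patient study appeared after dosing ended (Protocol 1.1.5.3). Counting SAEs for 42 days after the last dose is a defensible, conservative choice.
- **The information is not lost.** Listings of all SAEs, and of all events in patients who died, show start date and days since first dose (SAP 12.1.1, 12.1.7, 12.1.8). The listing of withdrawn patients gives days on IMP (SAP 7.2). Rough separation by hand is possible.
- **Not every table is pooled.** Weekly-dosing tables are limited to events during weekly dosing, and the dose-reduction table to the Treatment Period.
- **Follow-up will be incomplete.** Follow-up information on patients who withdraw consent goes only into the medical record (Protocol 8.5), and some patients will be lost, so 57.5 patient-years is an upper-end figure.
- **Nothing is concealed.** The pooling is stated openly and fits the protocol's open-ended TEAE definition. The study is descriptive and has no randomised comparator arm, so no randomised comparison is affected.

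These points limit the size of the matter. They do not explain why a period defined in 12.1.4 goes unused, or why counts and PYE with different windows share a table without a note.

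**Conclusion.** The point holds as one of presentation and matching windows. The main SAE and death figures are incidences over treatment plus up to 42 days, placed in Treatment Period summaries, beside a PYE that stops at the last dose and among non-serious events that stop at the last visit.

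On the planned percentage scale the effect is modest: about one percentage point at an assumed hazard of 0.10 per year. A rate formed from the overview would be 11.5% to 18.5% above the on-treatment rate, given equal hazard, complete follow-up and the exposure range above; the excess would be smaller or larger as the follow-up hazard is lower or higher. The documents support neither a claim that a planned rate is overstated nor a claim that the follow-up SAEs are off-drug events. They also give no reason to remove follow-up events from the TEAE tables: that would conflict with the protocol's definition and could drop delayed drug effects.

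**What to change.** - In SAP 12.1.1, 12.1.5 and 12.1.8, keep the combined total and add a split of SAEs and deaths by onset on treatment versus onset in follow-up.
- State one cut-off, last dose or last treatment visit, and use it for both the split and PYE.
- Footnote the overview to say that PYE excludes follow-up time. If any rate is reported, give it a denominator covering the same window as its events.
- Flag follow-up onsets in the TEAE tables; do not exclude them.
- Correct the cross-reference in 12.1.1 from 12.1.3 to 12.1.4.

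The cost is SAP wording, one extra column split and a footnote. A period allocation already exists in 12.1.4; if the last dose is chosen as the cut-off, the split needs one further derivation from dates already in the data. No new data are needed and no event is hidden.

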12.1.2 Classification of Adverse Events

Adverse events will be classified according to the time of onset of the adverse event (for handling of incomplete start dates, see section 19.3.5):

- *pre-study adverse event* – an adverse event that starts before the date of first dose of IMP in study 16159B.
- *treatment-emergent adverse event (TEAE)* – an adverse event that starts, increases in intensity compared to the preceding intensity, or changes from non-serious to serious on or after the date of first dose of IMP in study 16159B.

Handling of adverse events that increase in intensity or seriousness is further specified in section 19.4.2.

An adverse event is considered causally related to the use of the IMP when the causality assessment by the investigator is *probable* or *possible*.

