#### Medical

12. The patient has any other medical disease for which the treatment takes priority over treatment of schizophrenia or is likely to interfere with study treatment or impair treatment compliance.
13. The patient has a moderate or severe ongoing adverse event related to IMP from study 16159A considered of potential safety risk by the investigator.
14. The patient takes or has taken disallowed recent or concomitant medication (specified in [Appendix II](#)) in study 16159A.
15. The patient has a disease or takes medication that could, in the investigator’s opinion, interfere with the assessments of safety, tolerability or efficacy, or interfere with the conduct or interpretation of the study.
16. The patient has clinically significant abnormal vital signs considered of potential safety risk by the investigator.
17. The patient has one or more laboratory values outside the reference range, based on the last available blood or urine samples taken during study 16159A that are, in the investigator’s opinion, of potential risk to the patient’s safety, or the patient has any of the following values at study 16159A (the medical monitor should be contacted in case of uncertainty):
  - a serum creatinine value >1.5 times the upper limit of the reference range
  - a serum total bilirubin value >1.5 times the upper limit of the reference range
  - a serum alanine aminotransferase (ALT) or aspartate aminotransferase (AST) value >2 times the upper limit of the reference range
18. The patient has not previously been diagnosed with diabetes, but meets ANY of the following criteria (newly diagnosed diabetes) based on the last available blood samples taken during study 16159A:
  - HbA1C >6.5%, OR
  - fasting plasma glucose >126 mg/dL (7.0 mmol/L), OR
  - non-fasting plasma glucose >200 mg/dL (11.1. mmol).
19. The patient has previously been diagnosed with diabetes, but the condition is unstable as determined by ANY of the following criteria based on the last available blood samples taken during study 16159A:
  - HbA1c ≥7.0%, OR
  - glucose >6.94 mmol/L (fasting, >125 mg/dL) or 11.1 mmol/L (nonfasting, 200 mg/dL)

- any other abnormal laboratory tests that in the investigator’s clinical judgement are medically significant and would impact on the safety of the patient or the interpretation of the study results.

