12.1.9 Presentation of Adverse Events Leading to Withdrawal

All adverse events leading to withdrawal will be listed.

TEAEs leading to withdrawal for the APTS will be summarized by:

- SOC and preferred term
- preferred term and previous treatment

Treatment-emergent AEs leading to the withdrawal occurring while on weekly dosing will also be summarized by preferred term for the APTS.

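### Adverse events that began in 16159A and persist unchanged into 16159B are left out of the TEAE and AE-withdrawal summaries, even when they began on Lu AF35700 and cause withdrawal

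*SAP*

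**What the plan says.** SAP 12.1.2 sorts events by onset relative to the first dose in the extension. A pre-study event is "an adverse event that starts before the date of first dose of IMP in study 16159B". A TEAE is "an adverse event that starts, increases in intensity compared to the preceding intensity, or changes from non-serious to serious on or after the date"; what is meant is again the day on which extension treatment begins. SAP 12.1.4 uses the same cut-off for periods: the Lead-in Study Period takes "an AE that starts before first dose of IMP in study 16159B". Neither rule refers to the treatment received in 16159A.

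All eight summaries in SAP 12.1.6 are of TEAEs, and the summary tables in 12.1.8 are of treatment-emergent SAEs. In 12.1.9 the restriction is explicit: "TEAEs leading to withdrawal for the APTS will be summarized by" SOC and preferred term, and by preferred term and previous treatment. The third summary there, for weekly dosing, is also limited to treatment-emergent events.

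Events carried over from the lead-in study are in the extension database. Under Protocol Panel 2, footnote l, "ongoing adverse events from study 16159A and 16323A, respectively, are to be transferred by the investigator to the eCRF, when applicable". SAP 12.1.5 adds: "All adverse events will be listed for the APES, including a flag for TEAEs".

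**The concern.** A cut-off at first dose normally separates events before exposure from events during it. Here it does so only for patients who received risperidone or olanzapine in 16159A. Patients from the two Lu AF35700 groups go straight onto open-label Lu AF35700, with placebo in place of a taper (Protocol 6.1), and Protocol 3.2 presents this as continuing their treatment. For them, an event with onset before the cut-off may already be an event on the study drug.

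The primary objective is long-term safety and tolerability, and the primary endpoint in SAP 4.1 is adverse events, without a treatment-emergent qualifier. Whether adverse effects persist, and whether they eventually make patients stop, is part of what a 52-week extension should show. A patient must have completed 16159A to enter, so an event that leads to stopping in 16159B cannot have counted as a cause of withdrawal in the lead-in study. If the extension's AE-withdrawal summaries also leave it out, neither study tabulates it by preferred term as a cause of withdrawal.

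**Working it through.** No figure in the plan bears on this, so the check is to follow a carried-over event (onset in 16159A, ongoing at the first 16159B dose) through each output.

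**Can such events enter?** Yes. Exclusion criterion 13 for 16159A patients (Protocol 5.3) removes a patient only if "The patient has a moderate or severe ongoing adverse event related to IMP from study 16159A considered of potential safety risk by the investigator". Mild events, events judged unrelated, and moderate or severe related events not judged a safety risk can all come through.

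**Where does each kind of event appear?**

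1. *Unchanged or improving, no action taken.* Pre-study under 12.1.2 and Lead-in Study Period under 12.1.4. It is absent from all eight 12.1.6 tables and present in the full listing, without the TEAE flag.
2. *Worsens or becomes serious in 16159B.* It meets the second half of the TEAE definition, so it is in the 12.1.6 tables. There is no gap here.
3. *Unchanged, and leads to withdrawal.* It is absent from every 12.1.9 summary. It is present in the 12.1.9 listing, which covers all adverse events leading to withdrawal, and in the 7.2 table if recorded as a primary or other reason, because 7.2 has no onset restriction. Whether it is in the 12.1.5 overview is unclear (see below).
4. *Unchanged, and leads to dose reduction.* 12.1.10 refers to adverse events rather than TEAEs, so as worded the event can be counted. The reference there to the Treatment Period could apply to the event or to the reduction, so this is not certain.
5. *Already serious and not worsened.* It is absent from the 12.1.8 tables, present in the SAE listing, and in the 12.1.5 SAE count as worded.

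**Section 12.1.5 against itself.** The sentence on patient counts names TEAEs leading to withdrawal. The next sentence, on event counts, names adverse events leading to withdrawal. Read literally, case 3 adds to the number of events but not to the number of patients in the same overview table.

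**Tables that can differ.** If case 3 occurs, 7.2 can show more withdrawals for adverse events than 12.1.9. The listing would explain the difference; no table would.

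**Is there any summary of carried-over events?** None is specified. SAP 18 also drops the summaries against the 16159A baseline, so those will not supply the context.

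**The case against.** The strongest reply is that little is lost. The onset-based definition was set in advance in Protocol 17.9.1, and the SAP widens it by adding events that become serious. Every event is listed with preferred term, causality, intensity, action and outcome. Every withdrawal is counted by reason in 7.2, overall and by previous treatment. Several tolerability domains are reported without regard to AE onset: BARS global categories at baseline and by week, AIMS and mSAS scores, laboratory values, weight, vital signs and ECG. Akathisia that persists would show on the BARS. Events with onset in 16159A may also be reported in that study, whose analysis plan is not available here.

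Most of this stands, and it limits the point. The withdrawals themselves are not lost, and the TEAE definition need not change. What remains is that the reader of the tables cannot see which persistent events made patients stop. Somnolence, for example, has no scale to fall back on.

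Two stronger readings are tempting and are not supported.

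- *Such events are missing from every AE table.* They are not: worsened or newly serious events are TEAEs, and the 12.1.5 event counts and the 12.1.10 table are not worded as limited to TEAEs.
- *The rule makes continuing Lu AF35700 patients look better tolerated than RIS/OLZ switchers.* The same rule drops carried-over events in RIS/OLZ patients, including any that persist on Lu AF35700 and lead to withdrawal. Only three AE tables are split by previous treatment (SAP 12.1.1), no comparative test of AEs is planned, and patients coming from 20 mg/day change dose on entry. The net direction cannot be determined.

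**Conclusion.** The point holds in a limited form. A carried-over event that neither worsens nor becomes serious is outside the TEAE incidence tables, and outside the AE-withdrawal summaries if it causes withdrawal, even when it began on Lu AF35700. The two definitions in 12.1.5 need reconciling in any case. This is a cheap improvement to the reporting of a primary endpoint. It does not invalidate the planned analysis.

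The size is unknown, because the documents give no count of events ongoing at rollover. A reader might try to estimate it: if two thirds of 500 patients came from the Lu AF35700 groups (500 × 2/3 ≈ 333) and 5% to 15% carried an ongoing event, that would be about 17 to 50 patients (333 × 0.05 ≈ 17; 333 × 0.15 ≈ 50). Both shares are assumptions. The result would also include events that soon resolve or later become TEAEs, and it says nothing about withdrawals. The 33% somnolence and 11% akathisia in Protocol 1.1.5.3 do not help, since they are incidences in a 21-day study whose daily doses reached 30 mg, not persistence among completers. The number affected could be very small.

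**What to change.** 1. In SAP 12.1.5 and 12.1.9, summarise all adverse events leading to withdrawal from treatment in 16159B regardless of onset date, with TEAEs as a sub-row. Use the same definition for patient counts and event counts in 12.1.5.
2. Add one preferred-term table, by previous treatment group, of adverse events ongoing at the first 16159B dose, with their outcome at the end of treatment. Including all groups shows carried-over events from RIS/OLZ on the same footing as those from Lu AF35700.
3. Keep the TEAE definition for all other tables.

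The cost is SAP wording, revised withdrawal summaries and one extra table. No new data collection is needed, because ongoing lead-in events are already to be transferred to the eCRF. The downside is that AE-withdrawal counts may rise slightly; the TEAE sub-row still gives the count as now planned.
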